9.6.4. Clinical Study Report

The final clinical study report will be reviewed, audited, and approved by medical, clinical, statistical, and regulatory staff from the sponsor, and key study contributors from Lexitas.

9.6.5. Inter-Laboratory Standardization Methods

Not applicable. A single, qualified, and certified central clinical laboratory will be used to analyze and report clinical laboratory data.

9.7. STATISTICAL METHODS PLANNED IN THE PROTOCOL AND DETERMINATION OF SAMPLE SIZE

This section of the analysis plan describes the analyses explicitly mentioned in the protocol as well as additional analyses not explicitly mentioned in the protocol but planned prior to breaking the treatment mask. Section 9.8 describes any changes to analyses that were explicitly mentioned in the protocol or statistical analysis plan.

9.7.1. Statistical and Analytical Plans

General Conventions

Summary statistics for the data collected during this study will be presented to give a general description of the patients studied. Data from all sites will be combined in the computation of these descriptive summaries. Categorical variables will be summarized by the frequency and percentage of patients in each category. Continuous variables will be summarized using N, mean, standard deviation (SD), median, minimum, and maximum values.

Number of patients, minimums, and maximums will be calculated to the same number of decimal places as the source data. Means, medians, standard deviations, and quartiles will be calculated to one more decimal place than the source data. Percentages will be calculated to the nearest one decimal place. Zero count cells will be displayed as “0” with percentage of (0%). Unless otherwise noted, summaries will be performed by the treatment group and presented in the order of: AG-73305, 0.5 mg; AG-73305, 1 mg; AG-73305, 2 mg; AG-73305, 4 mg.

Baseline values will be defined as the last measurement prior to dosing of study medication. Ocular measurements will use the most recent measurement for each eye.

Numeric laboratory, pharmacokinetic, and immunogenicity data may be recorded at limits of detection (with a ‘<’ or ‘>’ sign, e.g., < 0.1 or > 0.1). To summarize laboratory data, the original value will be converted to one unit less or more at the level of measured precision (e.g. 0.4 in the case of < 0.5 and to 0.6 in the case of > 0.5). For pharmacokinetic data, for Time = 0 (predose), any result that is below the level of quantitation (BLQ) is set to zero; all other timepoints are set to missing for any computations. For immunogenicity, any titer < Value (a negative result) is set to zero. Summary tables for immunogenicity titer will not include these negative results.

The actual values will be presented in the data listings.

All data collected in this study will be presented in individual patient data listings for all patients.

Computations for all results will be performed using SAS (Version 9.4, SAS/STAT 15.2) computer software package (SAS Institute, Inc, 2013, 2020), unless otherwise specified.

Strata and Covariates

Not applicable.

Subgroups

Not applicable.

Multiplicity

Not applicable.

Missing Data and Outliers

Every attempt will be made to capture all study data. All analyses will utilize observed data only.

Visit Windows

The nominal visits listed in the eCRF will be used in the summaries. In general, unscheduled visits will not be summarized in tables unless otherwise noted.

Missing Dates

Missing dates that occur for prior or concomitant medications or adverse events will be queried for a date. If no date is obtained, the following imputation rules will apply:

- For start dates, if the given year (or year-month) is the same as study drug administration, the start date will be imputed as study drug administration date; otherwise, missing month-day (or day) will be imputed as '01-01' (or '01').
- For stop dates, missing months will be imputed as '12' and missing days will be imputed as the last day of the month. If this creates a date after discontinuation/completion, the date of discontinuation/completion will be used.

Imputed dates will only be used to classify events or medications, such as occurring before or after the start of treatment. Imputed dates will only be used in tables. Listings will display the available date data.

Interim Analysis

No formal interim analysis is planned. However, as the study is open-label, safety and efficacy data will be periodically reviewed and summarized for assisting the Safety Review Committee with their assessments.

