- Loss of > 5 ETDRS letters at 2 consecutive visits (one can be unscheduled) from a previous best study visit due to worsening of DME.

- An increase in CST  $> 75 \mu\text{m}$  from a previous best study visit which remains consistently  $> 75 \mu\text{m}$  from the previous best study in two consecutive visits, as assessed by SD-OCT. The later visit can be an unscheduled visit if determined to be necessary by the Investigator.
- An increase in CST  $> 50 \mu\text{m}$  from a previous best study visit, as assessed by SD-OCT and a loss of  $> 5$  ETDRS letters, which remains consistently  $> 50 \mu\text{m}$  and loss  $> 5$  ETDRS letters from the previous best study in two consecutive visits. The later visit can be an unscheduled visit if determined to be necessary by the Investigator.
- Progression of or worsening of proliferative diabetic retinopathy.

Patients will be followed for at least 4 weeks after Rescue medication administration or through Week 12, whichever is greater.

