- h. IOP measurement will be performed prior to and after AG-73305 injection at Baseline/Day1. After injection, IOP will be measured within 15 minutes using a tono-pen or tono-pen like device. If IOP >30mmHg, repeat IOP measurement at 15±5 minutes post injection until pressure is reduced
- i. Color fundus photos, OCT-A and SD-OCT images will be submitted to a reading center for grading; not required for eligibility
- j. OCT-A is to be performed at baseline and at the visit (OU) when **Rescue** treatment is given. OCT-A is to be performed prior to the rescue treatment
- k. Dilated fundus exam
- l. Prednisolone acetate 1% ophthalmic suspension will be provided to patients, who will be instructed to prophylactically treat the study eye QID 2 days prior to the Baseline visit. Patients will be instructed to taper based on the Day 2 follow-up visit
- m. Within 15 minutes following intravitreal injection, a post-injection assessment will be done, including checking for count fingers or hand motion vision
- n. At selected sites, blood (~10 mL) will be collected for plasma drug monitoring on Day 1 pre-dose (all Cohorts), 1 hour (Cohort 1 and 2 only), 3 hours (all Cohorts), 8 hours (all Cohorts) and 24 hours post dose (Cohort 3 and 4 only), Week 1 (all Cohorts), and Week 4 (all Cohorts) in approximately 2-4 patients.
- o. ~20 mL of blood will be collected on Day 1 pre-dose and Weeks 1, 4, 8 and 24 from all patients for anti-drug antibody assessments.

Additional examinations and unscheduled visits can be included as safety concerns arise.

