9.7.1.6.2. ETDRS BCVA

Descriptive summaries of the observed values at each scheduled visit as well as the change from baseline at each post-baseline visit will be presented for both eyes. Patients with a loss of ≥ 5 , ≥ 10 , and ≥ 15 letters in BCVA will be summarized by frequency and percentage.

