9.7.1.6.3. Intraocular Pressure (IOP)

Descriptive summaries of the observed values at each scheduled visit as well as the change from baseline at each post-baseline visit will be presented for both eyes. Patients with an increase of ≥ 10 mmHg in IOP will be summarized by frequency and percentage.

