9.7.1.6.7. Laboratory Evaluation (Hematology, Serum Chemistry and Urinalysis)

Descriptive summaries of the observed test results at Screening and Weeks 4, 12, and 24, as well as the change from baseline at Weeks 4, 12, and 24, will be presented for hematology, serum chemistry, and a subset of urinalysis labs. The frequency and percentage of patients with observed values of Low, Normal, High as well as the categorical shifts from baseline will be tabulated for hematology and serum chemistry labs. The percentages will be calculated based on the number of patients with baseline and post-baseline values at each visit in each treatment group. The frequency and percentage of patients with observed values for categorical urinalysis laboratory measurements will also be tabulated, with percentages calculated based on the number of patients with values at each visit in each treatment group.

It is expected that all samples will be analyzed by a central laboratory. If a local laboratory is used (such as for an unscheduled visit), the results will be included in the listings of laboratory data, but will not be included in descriptive summaries.

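### The counts of patients with BCVA loss and IOP rise omit pre-rescue values from unscheduled visits, so they can be understated but not overstated

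*SAP*

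**What the plan says.** SAP 9.7.1, under Visit Windows, states: "The nominal visits listed in the eCRF will be used in the summaries". It continues: "In general, unscheduled visits will not be summarized in tables unless otherwise noted".

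Two safety outputs count patients who cross a threshold:

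- SAP 9.7.1.6.2: patients losing at least 5, 10 or 15 "letters in BCVA will be summarized by frequency and percentage".
- SAP 9.7.1.6.3: patients with a rise of at least 10 "mmHg in IOP will be summarized by frequency and percentage".

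Neither sentence names the visits it draws on. In both subsections the preceding sentence is tied to the schedule: "Descriptive summaries of the observed values at each scheduled visit as well as the change from baseline at each post-baseline visit". Nothing elsewhere in 9.7.1.6 brings unscheduled visits back into a visit-based table. For laboratory data, 9.7.1.6.7 goes the other way: "If a local laboratory is used (such as for an unscheduled visit), the results will be included in the listings of laboratory data", and not in the descriptive summaries.

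The documents give two reasons for an unscheduled visit. The notes to the schedule in Protocol 1.3, repeated in SAP Appendix I, say: "Additional examinations and unscheduled visits can be included as safety concerns arise". The rescue criteria in the Protocol 1.1 synopsis, repeated in the SAP synopsis, allow one for confirming worsening: "The later visit can be an unscheduled visit if determined to be necessary by the Investigator".

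**The concern.** A by-visit mean needs a fixed set of visits, and nominal visits are the sensible choice for it. A count of patients who crossed a safety threshold answers a different question, namely whether the event was observed at all. For that count, a value should not be dropped because of the type of visit at which it was taken, least of all when both stated reasons for the visit make a poor value more likely.

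BCVA and IOP are listed safety assessments in both documents, and the study is meant to identify a maximum tolerated or highest administered dose. The cohorts are small, so a single patient missing from a threshold table changes how that dose level reads. SAP 9.7.1 also says safety data will be summarised periodically for the Safety Review Committee. If those summaries follow the same convention, they share the gap.

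**Working it through.** **1. Which rule governs the counts.** The default excludes unscheduled visits unless an exception is noted. SAP 9.7.1.6 to 9.7.1.6.10 note none, so the default applies to the BCVA-loss and IOP-rise counts. The SAP does not say whether the counts are made visit by visit or once per patient over follow-up. Either way, an unscheduled value has no place in the table.

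**2. Direction.** Let S be a patient's scheduled post-dose values before rescue and U the unscheduled ones. The patient is counted if the worst value crosses the threshold. The worst value over S and U together is at least as bad as the worst over S alone, so the count over S cannot exceed the count over S and U. With cohort size as denominator, the same holds for the percentage.

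**3. How a case drops out.** From the schedule, post-baseline visits fall on Days 2, 8, 28, 56, 84, 112, 140 and 168. Counted from Day 1, the gaps are 1, 6, 20 and then five of 28 days.

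- *IOP (hypothetical).* An eye has a rise of 10 mmHg at an unscheduled visit and is below that threshold at the scheduled visits. The table shows no rise. No rescue is involved.
- *BCVA (hypothetical).* A study eye with no earlier loss of 5 letters is 4 letters below baseline at Week 8 and 16 below at an unscheduled Week 10 visit. It is rescued the next day. The 16-letter value would count in all three categories (16 ≥ 15, 10 and 5). It is dropped because its visit was unscheduled. Later values are dropped by the rescue rule in SAP 9.7.1.6. The Week 8 value counts in none (4 < 5).

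**4. Weight of one patient.** SAP 9.7.2 gives 3–8 patients per cohort. One patient is 1/3 = 33.3, 1/6 = 16.7 or 1/8 = 12.5 percentage points.

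**5. Scale, under an assumption.** SAP Table 2 gives the chance of at least one case as 1 − (1 − p)^n. At p = 0.2 this is 1 − 0.8³ = 0.488, 1 − 0.8⁶ = 0.738 and 1 − 0.8⁸ = 0.832, as printed, and all 24 cells reproduce to rounding. Table 2 concerns DLTs and SAEs, so I borrow it only as a scale.

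Let q be the share of affected patients whose abnormal value appears only at an unscheduled visit. The documents do not give q. A scheduled-visit table then shows at least one case with probability 1 − (1 − p(1 − q))^n. With p = 0.2:

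| Assumed q | p(1 − q) | n = 3 | n = 6 | n = 8 |
|---|---|---|---|---|
| 0 | 0.20 | 0.488 | 0.738 | 0.832 |
| 0.10 | 0.18 | 0.449 | 0.696 | 0.796 |
| 0.25 | 0.15 | 0.386 | 0.623 | 0.728 |
| 0.50 | 0.10 | 0.271 | 0.469 | 0.570 |

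**The case against.** The best defence is that the information reaches the reader by other routes, and much of that stands.

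- *AE tables are not affected by the visit rule.* SAP 9.7.1.6.1 defines treatment-emergent events by start date, so an event found at an unscheduled visit and reported as an AE before rescue is tabulated. A reader might infer that every safety table excludes unscheduled visits; that is too broad.
- *The safety hypothesis names AEs as its measure*, by frequency and severity. A reader might infer that the test of that hypothesis is itself biased. The documents do not support that, because the two counts are supporting safety outputs.
- *Rescued patients remain visible.* SAP 9.7.1.5.2 tabulates rescue by visit and by reason and adds a Kaplan-Meier analysis. The BCVA patient above would appear as rescued under Week 8, though without the size of the loss.
- *Nothing is deleted.* SAP 9.7.1 lists all collected data for every patient, which is workable with about 25 patients.
- *The BCVA example depends on rescue being given on a later date.* If rescue is given at the same visit, SAP 9.7.1.6 sets that value to missing under its own rule, and counting unscheduled visits would not recover it. The IOP example does not have this dependence.

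These routes still leave the planned frequencies and percentages open to understatement. An IOP or BCVA value enters an AE table only if it is reported as an AE, and SAP 9.5.1.4.1 excludes DME worsening from AEs unless it exceeds what is expected. How often that exclusion would apply cannot be judged here, because the protocol's grading system and DLT definition are not in the available text.

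It can also be said that a count naming no visits is open to any visit. The default, however, asks for an exception to be noted, and none is. Keeping local-laboratory results out of central-laboratory summaries is a disclosed and defensible choice, and this point does not dispute it.

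**Conclusion.** The point holds for two outputs: the BCVA-loss and IOP-rise patient counts. Followed as written, the SAP leaves out pre-rescue values from unscheduled visits, and the counts can then only be unchanged or too low. This is a substantive rule rather than a missing detail, but other outputs soften its effect.

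Its size cannot be derived from the documents. What can be stated is the weight of one omitted patient: 12.5 to 33.3 percentage points in cohorts of 8 down to 3. For a true rate of 0.2, a cohort of 6 and an assumed q of 0.10 to 0.50, the chance that the table shows any case falls from 0.738 to between 0.696 and 0.469. That range illustrates an assumption and does not estimate this trial's loss.

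A reader might take the 28-day visit gaps as a measure of what is lost. They show only how easily scheduled visits can miss a short event. They say nothing about how often an unscheduled visit would have caught it. That omitted values tend to be worse is a reasonable inference from the stated reasons for these visits, not a documented figure.

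**What to change.** Keep by-visit summaries on nominal visits. In SAP 9.7.1 (Visit Windows), with matching text in 9.7.1.6.2 and 9.7.1.6.3, add wording such as:

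> By-visit descriptive summaries use nominal visits. The numbers of patients with a BCVA loss of ≥5, ≥10 and ≥15 letters and with an IOP increase of ≥10 mmHg are based on each eye's worst post-dose value at any scheduled or unscheduled visit, subject to the rescue-censoring rule in Section 9.7.1.6. The same counts from scheduled visits only are shown alongside. IOP measured immediately after injection on Day 1 is reported separately and does not enter the ≥10 mmHg count.

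The reference to 9.7.1.6 keeps the counts consistent with the other safety tables. The Day 1 clause is needed because the immediate post-injection reading belongs to the scheduled Baseline visit, so the present rule does not remove it, and it would otherwise enter a worst-value count.

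The cost is a short SAP amendment and one worst-value derivation for each measure, with no new data. The drawback is that patients with more visits have more chances to cross a threshold, which is why the scheduled-visit counts should stay beside the new ones. Laboratory handling need not change.

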9.7.1.3.3. Prior and Concomitant Medications

Prior and concomitant medications will be coded using the World Health Organization Drug Dictionary (WHODrug) (Version 2022-03, Lagerlund et al., 2020) for anatomical therapeutic chemical (ATC) classification and preferred drug name.

The frequency and percentage of patients with coded medications will be summarized by treatment group using the FAS. A patient who used multiple medications will be counted only once for each ATC and preferred drug name. Therapeutic Subgroup is sorted alphabetically, and preferred term is sorted by descending frequency overall within each Level 3 term according to:

1. Descending frequency within AG-73305, 0.5 mg;
2. Descending frequency within AG-73305, 1 mg;
3. Descending frequency within AG-73305, 2 mg;
4. Descending frequency within AG-73305, 4 mg;
5. PT in alphabetical order.

Prior and concomitant medications will be summarized separately. Ocular medications are defined as those medications for which an eye has been specified (OD, OS, or OU). Ocular and non-ocular medications will be summarized separately. Ocular medications will be summarized separately for study eye, non-study eye, and either eye.

Prior medications are defined as any medications that started and stopped prior to the first dose of study drug. Concomitant medications are defined as any medications that (1) start prior to the first dose of study drug and stop or are ongoing at or after the date of first dose of study drug; or (2) start at or after the first dose of study drug. Medications taken after Visit 9 or withdrawal from the study are not considered concomitant.

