9.7.1.6.1. Adverse Events

AEs are coded using MedDRA Version 25.0. Treatment-emergent adverse events (TEAE) are defined as events that start on or after the administration of study medication and up to the earliest instance of rescue therapy. Pretreatment adverse events are events that begin prior to administration of study medication. Ocular AEs are defined as those events for which an eye has been specified (OD, OS, or OU).

Ocular and non-ocular treatment-emergent AEs will be summarized separately. Ocular AEs will be presented by study eye and non-study eye and overall (OU) if an event occurs in either eye.

In all summaries of AEs, percentages are calculated based on the number of patients in each treatment group of the Safety Analysis Set.

Overall summaries of AEs by treatment will include:

- the number of AEs and SAEs reported;
- the number and percentage of patients who experienced any AE;

- the number and percentage of patients who experienced any serious adverse event (SAE) and the reason for seriousness;
- the number and percentage of patients with any AE by worst severity and worst relationship.

The overall summaries of TEAEs will also include the number and percentage of patients with any TEAEs leading to study termination.

Summaries of the frequency and percentage of patients with AEs by SOC and preferred term by treatment group will include:

- All AEs by SOC and preferred term;
- All AEs by SOC, preferred term, and maximum severity;
- All AEs by SOC, preferred term, and maximum relationship.

System organ class (SOC) will be sorted alphabetically, and preferred term (PT) within each SOC will be sorted by overall descending order of frequency according to the following rules in order:

1. Descending frequency within AG-73305, 0.5 mg;
2. Descending frequency within AG-73305, 1 mg;
3. Descending frequency within AG-73305, 2 mg;
4. Descending frequency within AG-73305, 4 mg;
5. PT in alphabetical order.

Patients are counted only once for each SOC and PT. In summaries of maximum severity and maximum relationship, patients with multiple occurrences of events will only be counted once at the maximum severity/relationship per SOC and PT.

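### The partial start-date rule ignores the stop date, so a medication known to have ended before dosing can be tabulated as concomitant (and, more rarely, a pre-dose event as treatment-emergent)

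*SAP*

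**What the plan says.** SAP section 9.7.1, Missing Dates, covers medications and adverse events, and imputation is the second step: "Missing dates that occur for prior or concomitant medications or adverse events will be queried for a date". If the query brings no date, and the known year (or year and month) of the start matches that of dosing, "the start date will be imputed as study drug administration date". Otherwise an unknown month and day become 1 January, and an unknown day becomes the first of the month.

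The stop-date rule is separate: "For stop dates, missing months will be imputed as '12' and missing days will be imputed as the last day of the month", capped at the date of completion or discontinuation. Neither rule refers to the other.

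The SAP then limits the purpose of these dates: "Imputed dates will only be used to classify events or medications, such as occurring before or after the start of treatment". They enter tables only, and listings show the dates as available.

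The classifications that use them are:

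- Section 9.7.1.3.3: "Prior medications are defined as any medications that started and stopped prior to the first dose of study drug". A medication is concomitant if it began before dosing and continued to or past the dosing date, or under the second limb, "2) start at or after the first dose of study drug". The second limb has no condition on the stop date.
- Section 9.7.1.6.1: TEAEs are "events that start on or after the administration of study medication and up to the earliest instance of rescue therapy". This too rests on the start date alone. Events that begin before dosing are called pretreatment events.

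**The concern.** Setting an uncertain start to the dosing date is sensible when the timing really is unknown. It stops being sensible when the record holds a stop date before dosing. That stop date shows that the medication or event both began and ended before the injection. The rule overrides this information, produces a record whose start is later than its stop, and sends it to the wrong side of dosing.

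The imputed dates exist only to place records before or after the start of treatment, so in these records the rule fails at its one task. At stake are the prior and concomitant medication tables and, to a lesser degree, the TEAE tables, in cohorts of 3 to 8 patients. Section 9.7.1 also says that safety data will be summarized periodically for the Safety Review Committee. A table produced exactly as specified could disagree with the listing behind it.

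**Working it through.** The plan gives no figure to reproduce here. The check applies the rules literally to test records.

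**Inputs from the documents**

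- Start and stop rules: SAP 9.7.1, Missing Dates.
- Definitions of prior, concomitant and TEAE: SAP 9.7.1.3.3 and 9.7.1.6.1.
- Medication look-back of 3 months before Screening: SAP 9.5.1.2.
- Screening from Day -30, extendable by 14 days: protocol section 1.3 and SAP Appendix I.
- Cohort size 3 to 8, tabulated at 3, 6 and 8: SAP 9.7.2.

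**Assumptions (illustrative)**: dosing on 15 September 2022 and completion on 2 March 2023. The completion cap binds in none of the records.

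| Record | Start given | Stop given | Start as imputed | Stop used | Class under the SAP | Class with a stop-date exception |
|---|---|---|---|---|---|---|
| A | 2022 | 10 Jul 2022 | 15 Sep 2022 | 10 Jul 2022 | concomitant / TEAE | prior / pretreatment (start 1 Jan 2022) |
| B | Sep 2022 | 14 Sep 2022 | 15 Sep 2022 | 14 Sep 2022 | concomitant / TEAE | prior / pretreatment (start 1 Sep 2022) |
| C | 2022 | Aug 2022 | 15 Sep 2022 | 31 Aug 2022 | concomitant / TEAE | prior / pretreatment (start 1 Jan 2022) |
| D | Jul 2022 | 20 Jul 2022 | 1 Jul 2022 | 20 Jul 2022 | prior / pretreatment | unchanged |
| E | 2021 | 10 Jul 2022 | 1 Jan 2021 | 10 Jul 2022 | prior / pretreatment | unchanged |
| F | 2022 | ongoing | 15 Sep 2022 | none | concomitant / TEAE | unchanged |
| G | 2022 | 1 Oct 2022 | 15 Sep 2022 | 1 Oct 2022 | concomitant / TEAE | unchanged |
| H | 2022 | Sep 2022 | 15 Sep 2022 | 30 Sep 2022 | concomitant / TEAE | unchanged |

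**Gap between stop and imputed start**

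- A: 21 days left in July + 31 in August + 15 in September = 67 days.
- B: 1 day.
- C: 15 days.

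A, B and C ended before dosing and are classed wrongly. D and E are classed correctly, because their known month or year differs from that of dosing. In F, G and H the stop date does not settle the timing, and the dosing date is the usual conservative choice.

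**Would record A be collected?** The earliest Screening is 30 + 14 = 44 days before dosing, about 2 August 2022, so the look-back opens about 2 May 2022. With the latest Screening, 2 days before dosing (13 September), it opens about 13 June 2022. A stop on 10 July lies inside the look-back in both cases.

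**Size**: one patient wrongly counted in one row of a cohort of n moves that row by 100/n points: 100/3 = 33.3, 100/6 = 16.7, 100/8 = 12.5.

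**The case against.** The strongest reply is that little depends on this rule. Sites are queried before anything is imputed. Imputed dates reach tables only, and the listings would expose a misplaced record. The summaries are descriptive, and the Week 4 BCVA endpoint does not use the rule. For missing or post-dose stop dates the default is conservative and right. All of this stands. It limits the severity, but it does not make the classification of records A to C correct.

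A reader might also infer three stronger things that the documents do not support.

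- **That adverse events are affected as much as medications.** Both schedules mark adverse event collection from Baseline, so an event that began and ended before the injection may seldom be recorded. Section 9.7.1.6.1 does define pretreatment events, so the case is possible but narrow.
- **That the error will be common.** The 3-month look-back means that medications stopped before dosing are in the data. The error also needs a failed query and a partial start in the dosing year or month. Nothing in the documents allows a rate to be estimated. Nor should the gap be exaggerated with stops early in the year: in the example, a general medication stopped before about 2 May 2022 falls outside the look-back.
- **That the percentages are an expected error.** Patients count once per SOC and preferred term, and once per ATC class and drug name. A misclassified record moves a row only if the patient has no other qualifying entry there, so the figures are per-row maxima.

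**Conclusion.** The point holds as a minor defect. Followed exactly, the start-date rule gives a wrong class to any record with a partial start matching the dosing year or month and a stop before dosing. Nothing else in the SAP text or in the protocol text available corrects it. The practical exposure is mainly in the concomitant medication table, which gains records that belong in the prior medication table. For adverse events the direction is an overstatement of TEAEs.

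The effect on any one row is at most 33.3, 16.7 or 12.5 points per patient at cohort sizes of 3, 6 and 8. The calendar dates are illustrative, but the mechanism does not depend on them. No efficacy conclusion is touched.

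**What to change.** Add one exception to the start-date rule in SAP section 9.7.1: where the stop date, as recorded or as imputed under the stop-date rule, is earlier than the day of dosing, do not use the dosing date; set an unknown month and day to 1 January of the given year, and an unknown day to the first of the given month.

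This names the replacement value. It corrects records A to C, leaves D to H as they are, and leaves no start after its stop in any of the eight. The conservative default remains wherever the timing is truly unknown. The cost is one SAP sentence and one condition in the derivation program, with no new data.
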